## **Schedule of Activities**

Clinical Trial Period	Screening	Baseline			Treatment		
Visit Number	-	V 1	V 2	V 3	V 4	V 5	V 6
Week & Window	W -4 to W 0	W 0 Day	W 4 ± 7 Days	W 8 ± 7 Days	W 12 ± 7 Days	W 16 ± 7 Days	W 24 ± 14 Days
Historical Spirometry (from patient's medical file)	X						
Informed Consent 	X						
Demographics/Medical History	X	X					
Donor-specific Antibody Test	X 				X8		X8
Inclusion/Exclusion	X	X (confirmation of screening)					
Serum/Urine Pregnancy Test 	X	$X^2$	X8	X8	X8	X8	X8
Physical Examination 	X	X	X	X	X	X	X
Vital signs 	X	X	X	X	X	X	X
Clinical Laboratory Tests	X	X 	X8	X8	X8	X8	X8
Spirometry 	X	X	X	X	X	X	X
Randomization		X					
L-CsA Administration 			Twice daily administration of 10 mg L-CsA				
Adherence via		]	Permanently throughout the complete clinical trial period (for Israel: after EoT)				
Blood Sampling (CNI, mTor inhibitors) 	X	X	X8	X8	X8	X8	X8
Concomitant Medication	X	X	X	X	X	X	X
Adverse Events		Permanent assessment throughout the complete clinical trial period					
Acute L-CsA Tolerability 		X					
Drug Accountability 			X	X	X	X	X
EQ-5D-5L		X			X		X

Clinical Trial Period		Treatment			Follow-Up
Visit Number	V7	V8	V9 / EoT	Remote Visit	V10 / EoS
Week/Month & Window	W 32 ± 14 Days	W 40 ± 14 Days	W 48 ± 14 Days	V 2 – V8	W 52
Donor-specific Antibody Test			X8		
Serum/Urine Pregnancy Test 	X8	X8	X8		X 
Physical Examination 	X	X	X		X
Vital Signs 	X	X	X		X
Clinical Laboratory Tests	X8	X8	X8		X8
Spirometry 	X	X	X	X	X
L-CsA Administration 	Twice daily administration of 10 mg L-CsA				
Adherence via CCI	Permanently throughout the complete clinical trial period (for Israel: after EoT)				
Blood Sampling (CNI, mTor inhibitors) 	X8	X8	X8		X 
Concomitant Medication	X	X	X	X	X
Adverse Events	Permanent assessment throughout the complete clinical trial period				
Acute L-CsA Tolerability 					
Drug Accountability 	X	X	X		
EQ-5D-5L			X		

NOTE: The Screening phase (time between screening and randomization visit) last from one day to up to 4 weeks.

5	At all visits, spirometry will be performed on the CCI	and on the CCI	as per Section 12.1.1.1. At the Baseline	Visit (V1), serial spirometry i	s to
	be performed prior to Randomization (CC) and CCI	CCI			after
	completion of L-CsA dose (or after Randomization to SoC). R	emote visits will be	e performed oci	. Visit 10 spirometry will be	
	performed in those patients not rolling over to Boston 3 on the	e cci only	7 .		

 Only in patients randomized to receive L-CsA treatment.

 Conduct prior to any screening activities.

[figure not shown]
<sup>2 Not more than 7 days prior to Randomization. Urine pregnancy test is allowed at Visit 1 only. Austria only: Urine pregnancy tests will be performed every month according to local law (Visits 5 through 9).

Including body weight, height (Screening Visit only), cardiovascular, respiratory, nervous, gastrointestinal, hepatic, renal, dermatological, musculoskeletal, extremities, eyes, ears, nose, throat, and lymphatic.

<sup>4 Including systolic and diastolic blood pressure (sitting, after 5 minutes of rest), pulse rate (sitting, after 5 minutes of rest), body temperature (the same method should be used for each patient and throughout the clinical trial), and respiratory rate.

- within 60 min. prior to next CNI (cyclosporine A and/or tacrolimus) administration. Blood levels of mTor inhibitors will be taken only if applicable, i.e., if patient is treated with mTor inhibitors.
-  ±3 days of the Visit date.
-  If a DSA test performed within 4 weeks before screening is available, a further DSA test at screening visit will not be mandatory.
- Laboratory tests at V1 are not mandatory in case laboratory tests at screening visit have been performed within 2 weeks from V1.

# **14.1 Clinical Trial Flow Chart**

# 14.2 Study Visits

# 14.2.1 Screening

Eligible patients who express interest in participating in the trial must sign an IRB/EC approved informed consent form (ICF) prior to initiation of any clinical trial activities. Patients who fulfill all of the inclusion criteria and none of the exclusion criteria may be enrolled into the clinical trial.

Documentation of the patient's consent and eligibility must be completed by the Investigator or his/her designee. All patients who fail the screening activities will be documented in the screening failure log.

The following screening activities will be performed during the screening period (up to 4 weeks prior to Visit 1):

- **Informed Consent:** Obtain informed consent prior to performing any clinical trial activities.
- **Demographics:** Year of birth, gender, ethnic group, date of body measurements, height and weight.
- Medical History: Details related to each patient's lung transplant will be recorded and will include: underlying condition (cause of lung failure), date, type of transplantation, donor demographics, donor cause of death, donor/recipient Human Leukocyte Antigen (HLA)-status, induction therapy, antiviral/antifungal/antibacterial therapy, cold ischemia time, donor/recipient CMV-status, donor/recipient Epstein Barr Virus (EBV)-status, acute lung injury. All other significant medical conditions (including GERD) and procedures (including past surgeries) occurring before the ICF is signed will be recorded as medical history. Females will be queried regarding their reproductive histories.
  - Confirmation of screening FEV1 above 51% of personal best FEV1 value post-transplant.
  - **Proof of diagnosis** will be recorded.
- **Donor-specific antibody assay:** Collect a blood sample for this assay at the Screening Visit. If DSA test performed within 4 weeks before screening is available, a further DSA test at screening visit will not be mandatory
- Inclusion/Exclusion Criteria: Evaluate eligibility for the clinical per the inclusion/exclusion criteria.
- **Serum Pregnancy Test:** Will be obtained in women of childbearing potential (see Appendix II). A serum or urine pregnancy test must be obtained within 7 days prior to randomization.
- **Physical Examination:** Body weight and height, cardiovascular, respiratory, nervous, gastrointestinal, hepatic, renal, dermatological, musculoskeletal, extremities, eyes, ears, nose, and throat, and lymphatic.
- Vital Signs: Blood pressure, heart rate, body temperature, respiratory rate.

- Clinical Laboratory Tests: All parameters listed in Section 13.1.5 of the protocol, to be performed in the local laboratory at the study site.
- Col Patients will be trained by site personnel on the use of this portable spirometer.
- CCI (on CCI ): FEV1, CCI , FVC, CCI ratio

  A spirometry assessment will be performed on CCI as per

  Section 12.1.1.
- Document historical spirometry data from personal best post-transplant prior to Screening, plus
  - Date of personal best FEV1 post-transplant and all lung function values available (FVC [absolute], FEV1 [absolute], occlude [absolute])
  - Dates of meeting BOS 0-p or BOS 1 criteria and all lung function values available (FVC, FEV1, CCI
- **Blood Sampling:** For determination of serum levels of calcineurin inhibitors and mTor inhibitors
- **Dosages of maintenance immunosuppression:** record on the Concomitant Medication eCRF
- Concomitant Medications/Therapies: Name of drug, dosage, duration
- Adverse Events

#### 14.2.2 Visit 1 / Baseline Visit

Baseline Prior to Start of Treatment

- Verify Informed Consent was obtained
- Verify Demographics/Medical History
- Verify Inclusion/Exclusion Criteria were met at the Screening Visit
- Repeat Serum (or Urine) Pregnancy Test, if result was obtained more than 7 days prior to the visit
- Physical examination
- Vital signs
- Clinical laboratory tests. Not mandatory in case laboratory tests at screening visit have been performed within 2 weeks from Visit 1
- CCI CCI Patients will be provided with the portable spirometer at the Visit 1 / Baseline Visit only if the patient will be randomized in the study
- Randomization
- Blood sampling for serum levels of calcineurin inhibitors and mTor inhibitors

- Concomitant medications/therapies
- Adverse events
- EQ-5D-5L Questionnaire

Start of Treatment

# Following activities will be performed (in patients randomized to L-CsA):

- Train patient on CCI use, drug storage and inhalation technique
- L-CsA Administration: only in patients randomized to receive L-CsA treatment. Supervise first inhalation.
- Activate column function in the clinical trial center
- Emphasize importance of adherence to IMP
- Emphasize importance of adherence to usual medications as taken prior to participating in the trial
- CCI (CCI ) at CCI after completion of IMP inhalation
- Queries about general health status
- Verify patient is familiar with drug administration and use of nebulizer device

Prior to release from clinic, adequate drug and the nebulizer system for home use will be dispensed to each patient.

# Following activities will be performed (in patients randomized to Standard of Care alone):

- Queries about general health status
- Emphasize importance of adherence to usual medications as taken prior to participating in the trial
- CCI (CCI only) at CCI after randomization

#### 14.2.3 Visit 2 through Visit 9 / EoT

- Physical examination
- Vital signs
- Clinical laboratory tests
- Serum pregnancy test (for Austria only: additional monthly urine pregnancy tests between the trial Visits 5 through 9)
- CCI (CCI ); if needed, refresher training for CCI
- L-CsA Administration
- Blood sampling serum levels of calcineurin inhibitors and mTor inhibitors
- Concomitant medications/therapies
- Adverse events
- Hospitalization

- Adherence via CCI
- Drug Accountability

### 14.2.4 Visits 1, 4, 6, and 9 / EoT

• Euro Quality of Life Questionnaire (EQ-5D-5L)

#### 14.2.5 Visit 10 / End of Study (EoS)

Only performed:

In patients not rolling over to Boston 3.

In patients who decided to withdraw the consent during the study (if possible) [see section 10.3.1]

- Physical examination
- Vital signs
- Clinical laboratory tests
- Serum pregnancy test
- CCI
- Blood sampling for serum levels of calcineurin inhibitors and mTor inhibitors
- Concomitant medications/therapies
- Adverse events
- Hospitalization

#### 14.2.6 Permanently throughout the complete clinical trial period

Adverse events

#### 14.2.7 Unscheduled Visits

Whenever medically warranted, the Investigator may ask the patient to appear or the patient may elect to appear at the clinic for an unscheduled visit. All medical measures performed as appropriate shall be documented in the Case Report Form for unscheduled visits.

#### 14.2.8 **Remote Visits (V2 - V8)**

Mandatory on site visits are Screening Visit, Visit 1 and Visit 9. Every effort will be made to have also all planned V2 to V8 and unscheduled visits at the study site. However, if one of these visits cannot be performed at site due to COVID-19, the site will schedule a remote visit with the patient according to the visit windows as defined in the Schedule of Activities. The scheduled time and the sequence of procedures (i.e. spirometry, IMP inhalation) should be the same as during on-site visits. The PI or Sub-Investigator and/or an appropriately qualified site study team member must call the patient to

- capture any potential adverse events (AEs) and to confirm the patient's status and wellbeing.
- capture any changes in concomitant medication
- check IMP supply with patient (if required re-supply needs to be arranged, see Section 9.7)

- provide refresher training for column if needed (for patients enrolled under protocol version 3.0 or later)
- guide the patient through a spirometry session using the column device (see Section 12.1.1.). Home spirometry should be scheduled around the same time as the usual clinic visits, whenever possible, to minimize the effects of circadian variation of lung function measurements (for patients enrolled under protocol version 3.0 or later).
- remind the patient to bring their column with them to their next clinic visit so that it can be checked and returned to them for continued use.
- remind the patient of IMP inhalation (to be performed after home spirometry assessment has been completed, for further details see also Section 12.1.1.4)

The PI or Sub-Investigator must confirm if, in their opinion, the patient is stable and suitable for prolonged home-treatment, and that patient is in agreement to continuing home-treatment until their next on-site study visit can occur.

All medical measures performed as appropriate shall be documented in the eCRF.

### 15 STATISTICS

This section presents an overview of the planned analyses. Final analyses are not limited to the summaries described herein. The Statistical Analysis Plan (SAP) will provide a detailed description of the planned statistical analyses and data summaries. If circumstances arise during the clinical trial that make these analyses inappropriate or if improved methods become available, the SAP may be revised. If discrepancies exist between the text of the statistical analysis as planned in the protocol and the final SAP, the final SAP will define the planned analysis of record. Reasons for such discrepancies will be described in the final Clinical Study Report (CSR).

This is a Phase III, prospective, multicenter, randomized, controlled trial with one blinded, adaptive interim analysis for sample size re-estimation and final identification of the model to be used for the primary analysis.

The primary outcome measure of the trial is the difference in mean FEV1 (mL) change from baseline to Week 48 between the L-CsA plus SoC and SoC alone groups CCI

For the purpose of this study, "baseline  $FEV_1$ " is the mean of the best  $FEV_1$  obtained at the Screening Visit and the best  $FEV_1$  obtained at the Baseline (randomization) Visit.

For all spirometer-based measurements see Section 12.1.1.

Data will be listed by patient and treatment group.

## 15.1 Analysis Data Sets

The following analysis data sets will be analyzed:

## Safety analysis set (SAFSet)

The SAF is defined as all randomized patients in the SoC group and all randomized patients receiving at least one dose of IMP in the L-CsA plus SoC group. All data collected after baseline to the end of clinical trial participation will be included in the safety summaries. Patients will be analysed according to the treatment they actually received.

## **Full analysis set (FAS)**

The FAS is defined as all randomized patients. Patients who receive augmentation of SoC therapy, are re-transplanted, or die before the first post-baseline assessment of the primary outcome measure will be retained in the FAS. Patients will be analysed according to the treatment group to which they were randomized.

A Data Review Meeting (DRM) will be used to determine if patients should be excluded from the FAS in cases of significant, major protocol deviations that would interfere with the assessment of treatment efficacy (e.g., patients not suffering from the condition under investigation).

## Per protocol Set (PPS)

The PPS is defined as all patients included in the FAS:

- who complete randomized treatment as scheduled or who are withdrawn prematurely due to lack of efficacy or lack of tolerability of the clinical trial treatment, and
- for whom no major protocol deviations interfering with the assessment of treatment efficacy are observed.

Eligibility for the analysis data sets will be determined in DRMs held after closing the database before the interim analysis and before the final analysis. Protocol deviations will be classified as 'major' when a significant influence on the assessment of the primary outcome measure for treatment efficacy cannot be excluded. Comprehensive justification for the classification of a protocol deviation as 'major' will be given in the DRM minutes as well as in the integrated CSR. Any exclusion of patients from the FAS will require individual justification.

The primary analysis of treatment efficacy will be performed in the FAS. An additional efficacy analysis in the PPS will be provided as a sensitivity analysis. Any data pertaining to safety and tolerability will be analyzed in the SAF.

# 15.2 Statistical and Analytical Methods

## 15.2.1 Descriptive Statistics

The data recorded in the case report forms will be summarized as appropriate, per treatment group and for the total group, using the following descriptive measures:

- All continuous study assessments will be summarized using descriptive statistics (i.e., n, mean, standard deviation, median, Q1, Q3, minimum, and maximum).
- All categorical study assessments will be summarized by time point, as applicable, using frequency counts and percentages.
- Discrete ordinal or higher-level data will be summarized as continuous data, but a tabulation of categories may be included additionally depending on the number of categories.

For all measures analyzed descriptively (i.e., measures to characterize the treatment groups and their baseline status, efficacy, and safety outcomes), tabulations comparing the treatment groups will be prepared. For outcomes measured more than once, the analyses will include tabulations of the measured values by visit as well as an analysis of change from baseline. Where provided, all confidence intervals will be two-sided 95% confidence intervals.

## 15.2.2 Characterization and Baseline Comparability of Treatment Groups

The number and percentage of patients who complete and discontinue the study treatment and the number and percentage of patients who complete and discontinue the clinical trial as well as reasons for early discontinuation (of both study treatments) will be presented.

Descriptive statistics will be presented for demographic, anthropometric, medical history, and antibody-response data.

## 15.2.3 Analysis of Efficacy

#### 15.2.3.1 Primary endpoint

#### Analysis population and estimand

FEV1 data collected from the on site CCI spirometer will be considered primary, while the data collected with the CCI home spirometer will be used for supportive analyses.

The primary efficacy parameter is the difference in mean FEV1 change from baseline to Week 48 between L-CsA plus SoC and SoC alone in the FAS population. Intercurrent events will be ignored, in line with the "treatment policy strategy" (ICH E9 addendum on estimands and sensitivity analysis in clinical trials to the guideline on statistical principles for clinical trials). After intercurrent events such as stopping treatment with L-CsA, augmentation of SoC therapy etc., FEV1 measurements will still be collected and used in the analysis. Intercurrent events preventing the use of FEV1 measurements after the event are death, re-transplantation, and withdrawal of the patient's consent. It is anticipated that these events will be rare in this patient population. The estimand will be estimated as if these events had not happened, i.e., the unobserved FEV1 data of such patients will be modeled until the scheduled end of treatment at Week 48.

#### Working hypothesis

The alterative hypothesis (H1) for this trial is that L-CsA plus SoC is superior to SoC alone in preserving FEV1, i. e., under H1 it is expected that patients treated with L-CsA plus SoC will exhibit a smaller mean FEV1 decline between baseline and the end of Week 48 than those who receive SoC alone.

#### The analysis model

The primary efficacy analysis will be carried out with a linear mixed model (LMM) for repeated measurements, using all available FEV1 measurements. The dependent variables are the absolute change from baseline of FEV1 measurements at visits 2 (i. e., the first post-baseline visit) to 9 (Week 48).

A flexible and robust model will be chosen for the random part of the LMM according to a prespecified stepwise procedure as described in detail in the SAP. The fixed part of the LMM is specified as follows. Time will be represented in a flexible and robust way using cubic splines, as described in detail in the SAP. The model will contain the following covariates (apart from the

intercept): time splines, treatment, the interactions of time splines by treatment, baseline  $FEV_1$ , the interactions of time splines with the baseline  $FEV_1$ , region (North America versus all other countries together), age (< 55 versus  $\geq$  55 years), and use of azithromycin at randomization. The primary efficacy estimand will be estimated from the model as the adjusted difference between groups in mean  $FEV_1$  change from baseline after 48 weeks. The one-sided p-value and the two sided 95% confidence interval will be provided. Superiority of L-CsA will be demonstrated by a statistically significant result (defined as p<0.025, one-sided) in favor of the L-CsA plus SoC treatment.

[figure not shown]
In case few data are collected at intermediate timepoints between baseline and Week 48 (see section 15.3 on interim analysis), the LMM model will be replaced by an ANCOVA model on the changes in FEV1 from baseline to Week 48, using the same stratification factors and the same covariates described for the LMM

## Sensitivity analyses

Intercurrent missing values and values missing due to death, re-transplantation and withdrawal of consent are assumed to be Missing At Random (MAR). Sensitivity analyses to the MAR assumption will be performed using different approaches, including selection modelling, simultaneous modelling of repeated FEV1 outcome and time to drop out, and controlled missing values imputation, and an analysis where re-transplantation and death are included in the definition of outcome variable and estimand as worst outcomes.

In addition to use of LMM to analyze the primary endpoint, simple t-test comparing the difference in mean FEV1 change from baseline to Week 48 between the treatment group in the FAS population including a 95% confidence interval for the treatment difference of the mean FEV1 change between the two treatment groups will be performed.

Further sensitivity analyses will be described in the SAP.

CCI

## 15.2.3.3 Type I error level control

The over-all type I error rate of the clinical trial will be  $\alpha = 0.025$  one-sided, corresponding to  $\alpha = 0.05$  two-sided.

[figure not shown]
Strong control of the clinical trial-wise type I error level will be achieved by a-priori ordering of hypotheses:

1. The primary endpoint (mean change in FEV1 from baseline to Week 48) will be tested first.

2.	CCI	

All tests will be performed using a local type I error level of  $\alpha = 0.025$  (one-sided).

If testing stops due to failure to reject a null hypothesis on a particular level of the hierarchy, all lower level tests will still be performed but will be considered descriptive.

#### 15.2.4 Cumulative Maintenance Immunosuppression

The total immunosuppression administered from the day of randomization will be evaluated. At each trial visit, the doses of calcineurin inhibitors (e.g., tacrolimus), antimetabolic agents (e.g., mycophenolate mofetil), and corticosteroids will be recorded by the Investigator on the concomitant medications eCRF. The cumulative dose of maintenance immunosuppressive treatment will be summarized for each group and compared descriptively.

#### 15.2.5 Analysis of Safety

Safety outcomes are listed in Section 13.1. All safety measures will be compared descriptively between the treatment groups in accordance with the concept of descriptive data analysis in the SAS population. Treatment group comparisons of safety outcomes will be based on statistical tests and confidence intervals (if applicable).

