## 15.5 Sample Size Considerations

The initial sample size was based on the following consideration. Assuming a treatment group difference for mean FEV1 change from baseline of 200 mL and a standard deviation of 350 mL at the end of treatment Week 48, an independent samples t-test with a one-sided type I error level of  $\alpha$ =0.025 will have at least 80% power to reject the null hypothesis when the sample size in each treatment group is at least 50 patients. To compensate for a loss of power due to premature withdrawals, a total of 110 patients will initially be randomized.

Results of the interim analysis have been presented in Section 15.3.

Following FDA recommendation to obtain an adequately sized safety database for L-CsA inhalation and reach the originally planned sample size for BOSTON 1 and 2 studies combined, randomization will be stopped upon achievement of a total of approximately 220 patients in the present BOSTON-2 and BOSTON-1 studies.

Since the BOSTON-1 study is experiencing serious enrolment delay, it is anticipated that approximately 160-170 patients will be randomized in the present study and 50-60 patients in BOSTON 1. This sample size will provide a more reasonable power for the planned sensitivity analyses, including ANCOVA, for the present study (BOSTON-2).

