#### 8 STATISTICAL CONSIDERATIONS

### 8.1 General Considerations and Descriptive Statistics

All report outputs will be produced using version 9.2 or later, in a secure and validated environment. All tables, figures and data listings (TFLs) to be included in the report will be independently checked for consistency and integrity.

The data recorded in the eCRF will be summarized as appropriate, per treatment group and for the total group, using the following descriptive measures:

- All continuous variables will be summarized using descriptive statistics (i.e., n, mean, standard deviation (SD), median, Q1, Q3, minimum, and maximum).
- All categorical variables will be summarized by using frequency counts and percentages.
- Discrete ordinal or higher-level data will be summarized as continuous data, but a tabulation of categories may also be included, depending on the number of categories.
- For time-to-event variables, cumulative event-free survival times will be evaluated using
  the Kaplan-Meier method. A frequency table showing the number of events and censored
  patients by treatment group, will be presented along with the event-free rates (and twosided 95% confidence). Kaplan-Meier graphs will be presented along with the number of
  patient-at-risk at exact time points. If different rules are not specified, patients who are free
  from event will be censored at the study termination.

For all measures analyzed descriptively (i.e., measures to characterize the treatment groups and their baseline status, efficacy, and safety outcomes), tabulations comparing the treatment groups will be prepared. For outcomes measured more than once, the analyses will include tabulations of the measured values by visit, as well as change from baseline. Where provided, all confidence intervals will be two-sided 95% intervals.

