#### 15 SAFETY DATA

#### 15.1 General Considerations

Summaries of safety data (e.g., AEs, laboratory data, vital signs) will be provided for the SAF. No inferential analyses are planned for safety endpoints.

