#### 15.3 Adverse Events

All AEs occurring during the clinical trial, whether or not attributable to study treatment, will be documented in the eCRF. All AEs will be coded to SOCs and PTs using the MedDRA dictionary (version 23.1).

Treatment-emergent adverse events (TEAEs) are defined as AEs with onset on or after the date of randomization.

The Investigator will assess the relationship (unrelated, possible, definite) of each AE to the clinical trial treatment assignment (L-CsA plus SoC or SoC alone). Treatment-related AEs are defined as events the Investigator considers to be possibly or definitely related to clinical trial treatment assignment.

All AEs reported in the eCRF will be presented in by-patient listings for the SAF.

The following summaries will be presented for AEs by treatment group and overall:

- Overview table including the number and percent of patients with:
  - o AEs,
  - o TEAEs.
  - o TEAEs leading to discontinuation of study treatment,
  - o TEAEs leading study discontinuation,

Final Version 5.0 Page 61 of 76

- o TEAEs leading to death.
- o TEAEs by severity (Mild, Moderate, Severe),
- o Study treatment related TEAEs,
- o Serious TEAEs,
- Serious study treatment related TEAEs;
- TEAEs, grouped within SOC by decreasing frequency of PT;
- TEAEs by decreasing frequency of PT;
- TEAEs leading to discontinuation of study treatment, grouped within SOC by decreasing frequency of PT;
- TEAEs leading to study discontinuation, grouped within SOC by decreasing frequency of PT;
- TEAEs leading to death, grouped within SOC by decreasing frequency of PT;
- TEAEs by maximum severity, grouped within SOC by decreasing frequency of PT;
- TEAEs by relationship, grouped within SOC by decreasing frequency of PT;
- Serious TEAEs, grouped within SOC by decreasing frequency of PT;
- Related serious TEAEs, grouped within SOC by decreasing frequency of PT.

Patients who have multiple events coded to the same PT or within the same SOC will be counted only once in the patient counts for the corresponding summaries, but all events will be considered and listed. Table presentations will contain counts of patients, percentages of patients, and the number of events.

Any AE with missing relationship will be assumed related and summarized in the possible related category to clinical trial treatment assignment. Patients who experience the same event multiple times will be included in the most related category for summarization.

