#### 15.3.1 Infections

All infections will be reported as AEs on the AE eCRF. The summaries described in this section will be provided for treatment-emergent infections (defined as for TEAEs). Treatment-emergent infections will be summarized on the basis of information reported on the AE eCRF.

For any infection, the following summaries will be presented by treatment group:

- Number (percent) of patients with at least one infection,
- Number and % of infections per patient (0, 1, 2, ...),
- Descriptive statistics for number of infections per patient.

The number of infections per patient and per patient-years (cumulative follow-up of each patient) will be provided by year (e.g., 2019, 2020, 2021, etc.) and overall.

A by-patient listing summarizing information on infections will be provided on SAF set.

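### Protocol 15.2.5 and SAP 15.1 disagree on safety inference, and no readable SAP safety section plans a between-arm contrast or confidence interval

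*Protocol*

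**What the plan says.** **Protocol 15.2.5** has two sentences that pull in different directions. The first is "All safety measures will be compared descriptively between the treatment groups". The second is "Treatment group comparisons of safety outcomes will be based on statistical tests and confidence intervals (if applicable", so it ends with a qualifier.

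**SAP 15.1** resolves this on the descriptive side: "No inferential analyses are planned for safety endpoints". The rest of the safety chapter (SAP 15.3 to 15.8) follows suit:
- For adverse events: "Table presentations will contain counts of patients, percentages of patients, and the number of events".
- For infections there is also an exposure-adjusted figure: "The number of infections per patient and per patient-years (cumulative follow-up of each patient) will be provided by year", and overall. No interval or between-arm ratio goes with it.
- Laboratory values and vital signs get summary statistics by visit and arm. Physical examinations and antibody tests are listed only.

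**SAP 8.1** sets the level of any interval but does not require one for safety: "Where provided, all confidence intervals will be two-sided 95% intervals".

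**Precedence.** Where protocol and SAP differ, Protocol section 15 says "the final SAP will define the planned analysis of record", and it leaves the reasons to the clinical study report. The readable entries of SAP section 16 (changes from planned analyses) include one on the safety set definition and none on safety comparisons. Other entries there are blacked out.

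**The concern.** The trial objective in both documents is efficacy and safety. Two arms with similar percentages for an event can look reassuring while the data still allow a material excess on L-CsA. An interval for the between-arm difference is the ordinary way to show how much excess has not been excluded. The protocol provides for such intervals, qualified by applicability, and the incidence of serious events, infections or malignancies is a case where an interval plainly applies. Because the SAP governs, the report as planned need not contain any.

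The SAP is not sparing with between-arm statistics elsewhere. Section 12.1 plans Fisher's exact p-values for use of basic immunosuppressants by class and by time interval. That is medication use and not a safety outcome, but it leaves the plan with formal comparisons of background drugs and none for deaths, serious events, infections, malignancies or renal events.

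**Working it through.** **1. The text.** Protocol 15.2.5 provides for tests and intervals where applicable. SAP 15.1 plans no inference. These differ on tests outright. On intervals the SAP is silent: it does not forbid a descriptive one, but no readable safety section schedules one.

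**2. The plan's own figure.** The documents state no precision for safety. The only sample size is for efficacy (Protocol 15.5; SAP 8.2): 200 mL, SD 350 mL, one-sided 0.025, 80% power. By the normal formula, n = 2 × (1.960 + 0.842)² × (350/200)² = 48.1, so 49 per arm. The exact t-test gives 49.05, so 50. The stated 50 per group reproduces and is not in dispute.

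**3. Inputs for safety precision.**
- 169 randomized (SAP 8.2), allocated 1:1 (Protocol synopsis).
- The split is not given; 84 on L-CsA and 85 on SoC is assumed. The safety set is analysed by treatment received, so the real denominators may differ.
- Event risks are not given; 10%, 20% and 40% in both arms are assumed.

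**4. Formula.** Newcombe interval for d = p1 − p2, with Wilson limits (l, u) for each arm:
- lower = d − √[(p1 − l1)² + (u2 − p2)²]
- upper = d + √[(u1 − p1)² + (p2 − l2)²]

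**5. One case in full, 17/84 against 17/85.** p1 = 20.24% (Wilson 13.04 to 30.04) and p2 = 20.00% (12.88 to 29.72), so d = 0.24.
- lower = 0.24 − √(7.20² + 9.72²) = −11.9 points
- upper = 0.24 + √(9.80² + 7.12²) = +12.4 points

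**6. Results.**

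| Events, L-CsA v SoC | Observed risk, about | 95% CI for difference (points) |
|---|---|---|
| 8/84 v 8/85 | 10% | −9.2 to +9.5 |
| 17/84 v 17/85 | 20% | −11.9 to +12.4 |
| 34/84 v 34/85 | 40% | −14.0 to +15.0 |
| 0/84 v 0/85 | 0% | −4.3 to +4.4 |

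With the arms swapped (85 on L-CsA, 84 on SoC) the upper limits for the first three rows are 9.2, 11.9 and 14.0. At a 10% risk the interval for the risk ratio reaches about 2.5.

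**7. Infection rate.** Full 48-week follow-up gives 84 × 48/52 = 77.5 and 85 × 48/52 = 78.5 patient-years. At an assumed one infection per patient-year in both arms, the half-width on the log scale is 1.96 × √(1/77.5 + 1/78.5) = 0.314, so the rate ratio interval is 0.73 to 1.37. This is Poisson; repeat infections in the same patient would widen it.

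**The case against.** A good deal of the opposing case stands.

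- **The protocol is not a clear commitment.** A reader might infer that it promises intervals which the SAP then withdraws. The documents do not support that: the sentence is qualified, and the one before it calls the comparison descriptive.
- **The tables are not empty of information.** A reader might infer that they carry no measure of excess at all. But counts and percentages by arm are planned, infections are also given per patient-year, and a crude interval can be computed from these. What is lost is display, and advance choice of outcomes and method.
- **Section 16 proves little.** With entries redacted, one can say only that no readable entry records the change. The protocol also names the study report as the place for reasons.
- **The safety database.** It is tempting to argue from "Following FDA recommendation to obtain an adequately sized safety database for L-CsA inhalation" that this SAP should state the precision which that database delivers. That target is about 220 patients in BOSTON-1 and BOSTON-2 combined, and this SAP covers BOSTON-2 alone. The intervals above are not the precision of the combined database.
- **Descriptive safety analysis is legitimate.** With many unpowered outcomes, unadjusted intervals may be read as informal tests, and simple risk differences ignore unequal follow-up. An unblinded data monitoring committee also reviews safety by arm during the trial.

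None of this removes the mismatch between the documents, nor the case for a few pre-specified intervals. A descriptive approach and a confidence interval are compatible, and committee review during the trial does not tell readers of the report what has been excluded.

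**Conclusion.** The point holds in a limited form. The two documents differ on whether safety comparisons involve inference, the SAP prevails, and no readable safety section plans a between-arm contrast or interval. At the size of this trial, equal observed risks of 10% to 40% leave room for a true excess on L-CsA of about 9 to 15 percentage points, which the planned tables do not display. The size rests on an assumed split of 84 to 85 and on assumed event risks; the 169 is from the SAP.

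The primary efficacy analysis, data collection and monitoring of patients are unaffected. This is an inconsistency to reconcile and an inexpensive improvement in reporting. It is not evidence that a safety signal would be missed.

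**What to change.** In SAP 15.1, keep the absence of hypothesis tests and add two-sided 95% confidence intervals, labelled descriptive and unadjusted for multiplicity, as follows.

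1. **Risk difference** (L-CsA plus SoC minus SoC; Newcombe or Miettinen-Nurminen, one chosen in advance) for a fixed list the SAP already tabulates:
   - serious TEAEs
   - TEAEs leading to death
   - TEAEs leading to discontinuation of study treatment (only where the comparison is meaningful, since the control arm has no L-CsA to stop)
   - TEAEs leading to study discontinuation
   - at least one infection
   - any malignancy
   - each of the three renal preferred terms in SAP 15.6
2. **Infection rate ratio** per patient-year, by a method that allows for overdispersion. This also takes account of unequal follow-up for that outcome.
3. **Mean difference** in creatinine change from baseline at Week 48.

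Record the remaining departure from Protocol 15.2.5, that no p-values are given, in SAP section 16 with its reason.

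**Cost:** a paragraph of SAP text and a few added table columns. It needs no new data and uses no alpha. The downside is that unadjusted intervals may be read as tests, so the label must appear on each table.
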